#### **4.1.3 Exploratory Endpoints (at Investigator Discretion)**

## 4.2 Study Design

PQ-110-002 study is an open-label extension study to evaluate the safety, tolerability, efficacy, and pharmacokinetics of QR-110 in subjects with LCA due to c.2991+1655A>G mutation (p.Cys998X) in the *CEP290* gene.

Subjects will be given the opportunity to enroll into the extension phase study PQ-110-002 for continued dosing if available data support current and/or future benefits for the subject from QR-110 treatment. The decision will be based on the assessment of individual subject's benefit/risk based on individual data and data from QR-110 clinical studies. The Investigator, in consultation with the Medical Monitor, will decide on enrollment of each individual subject, as well as on dosing of the first treated eye and treatment initiation of the contralateral eye. Continued subject treatment in this study is desirable, but cannot be guaranteed, since it will depend on the risks and benefit of further treatment on a case-by-case basis, as discussed and agreed upon with the Medical Monitor.

Dose modifications or modifications of the dosing interval will be considered on the basis of emerging safety and/or efficacy data and if it is anticipated to be in the best interest of the subject.

The contralateral eye and the first treated eye will be injected 3 months apart. The injection interval of 3 months between both eyes allows thorough safety evaluation and will decrease subject burden, with a 3 month-visit frequency during the course of the study. This between-eye interval could be adapted if safety data are supportive, and for logistic reasons, and in agreement with the Medical Monitor. The same safety monitoring protocol and efficacy assessments will apply to both eyes.

QR-110 will be administered via IVT injection in accordance with the procedures outlined by the American Academy of Ophthalmology ([Avery 2014](#)).

A program-specific review of safety, which may include independent experts, will be in place to assess emerging data from clinical studies on an ongoing basis.

Baseline functional and structural measurements for the first treated eye will be those from study PQ-110-001. Baseline functional and structural measurements for the contralateral eye will be those from the Screening/Day 1 visit of the current study which is the last visit of study PQ-110-001 (see [Section 4.2.1.1](#)).

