##### 4.2.2. Treatment Groups for Analysis

Safety and efficacy data will be summarized by treatment group. The first treated eyes data will be summarized based on the treatment group allocation in study PQ-110-001. The subjects who started with 320/160 µg in study PQ-110-001 will be moved to 160/80 ug group in study PQ-110-002; other subjects who started with 160/80 µg in study PQ-110-001 will continue the same dose in study PQ-110-002. The contralateral eyes data will be summarized for treated and non-treated for the overall study

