### 4.2.4. Definition of Baseline

For the endpoints collected on the subject level, the screening visit value in study PQ-110-002 will be defined as Baseline 002 values. For the endpoints collected on the eye level, there are three types of baseline values used for study PQ-110-002:

- Baseline 001: for BCVA, it is defined as  
for mobility course and FST, the average of measurements at pre-dose in study PQ-110-001 is considered as baseline 001.
- Baseline 002: for BCVA, it is defined as  
; for mobility course and FST, it's defined as the average of last two measurements only if the interval between them is up to 1 month before entering study PQ-110-002. Otherwise the most recent value will be taken as baseline 002. For the other endpoints, the screening value in study PQ-110-002 is used as baseline 002 value.
- Pre-dose Baseline: the efficacy endpoints collected on the eye level except BCVA, mobility course and FST, the baseline 002 will be used. For BCVA, mobility course and FST, Baseline 001 values are used for the first treated eye, non-treated contralateral eye as well as both eyes. For treated contralateral eye,
  - For BCVA, the baseline result corresponds to the best of the two most recent BCVA values available before the first dose of treatment with sepofarsen in that respective eye

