## Statistical Analysis Plan Template

Sponsor:	ProQR Therapeutics		
Protocol:	PQ-110-002		
Document Version No.:	1.0	Document Date:	04 JAN 2022

in study PQ-110-002 (in a maximum time-window of 1 month before dosing). If only one observation is available on or prior to the subject's first dose, that observation will be used as the pre-dose baseline value. For mobility course, FST and OCT, the data most recently collected prior to the subject's first dose of study treatment in study PQ-110-002 will be used as the pre-dose baseline value.

- For other efficacy endpoints collected on the eye level, the baseline 002 will be used.

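### For BCVA, mobility course and FST, the SAP's Pre-dose Baseline measures treated and non-treated contralateral eyes from different studies, so their changes at the same visit cover different lengths of time.

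*SAP*

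**What the plan says.** SAP 4.2.4 defines three baselines for eye-level endpoints: Baseline 001, Baseline 002 and a Pre-dose Baseline. The Pre-dose Baseline for BCVA, mobility course and FST depends on the eye.

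- Non-treated contralateral eye: "Baseline 001 values are used for the first treated eye, non-treated contralateral eye as well as both eyes". For mobility course and FST, "the average of measurements at pre-dose in study PQ-110-001 is considered as baseline 001". The BCVA definition of Baseline 001 is missing from the public text.
- Treated contralateral eye, BCVA: "the best of the two most recent BCVA values available before the first dose of treatment with sepofarsen in that respective eye" in PQ-110-002, "in a maximum time-window of 1 month before dosing".
- Treated contralateral eye, mobility course and FST: the latest reading before the subject's "first dose of study treatment in study PQ-110-002 will be used as the pre-dose baseline value". This is worded as the subject's first dose, not that eye's.

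For the rest the rule is "the efficacy endpoints collected on the eye level except BCVA, mobility course and FST, the baseline 002 will be used", so NIRAF, OCI and PLR use one PQ-110-002 reference for both groups of contralateral eyes.

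On presentation, SAP 4.2.2 says "The contralateral eyes data will be summarized for treated and non-treated for the overall study" population. SAP 4.8.1.1 tabulates BCVA change from baseline by visit for first treated, treated contralateral and non-treated contralateral eyes.

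Protocol 4.2 says: "Baseline functional and structural measurements for the contralateral eye will be those from the Screening/Day 1 visit of the current study". Protocol 10.1 says the same in substance, and neither section separates treated from non-treated eyes. SAP section 5 declares a change to the baseline definition relevant to PQ-110-001 but gives no reason for the split.

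**The concern.** A reader of the BCVA table will compare the treated and non-treated contralateral rows at the same visit. If those rows use the Pre-dose Baseline, the non-treated row also carries whatever happened during the parent study and up to entry here. The treated row does not.

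Protocol 2.0 describes slow progressive loss of remaining vision. Any such loss during the extra interval would enter the non-treated change only and make treated eyes look better. Learning on the mobility course or FST since the parent study would enter the same row and make treated eyes look worse. Neither is an effect of treatment in this study. With at most 11 subjects and no model planned, nothing later in the analysis would correct for the difference, and the tabulated means are likely to be taken at face value.

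**Working it through.** The plan has no figure to reproduce: the sample size is set by availability and the analyses are descriptive. The check is of elapsed time.

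**Inputs**

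- V: months from PQ-110-002 entry to the visit. Tables are by scheduled visit (SAP 4.2.10); V = 12 is used here.
- D: months from Baseline 001 to PQ-110-002 entry. Not stated in the documents; assumed 6, 12, 18 or 24.
- L: months from entry to the dose that fixes the treated eye's baseline. For BCVA this is that eye's own first dose; for mobility course and FST it is the subject's first PQ-110-002 dose. Protocol 7.2 schedules the contralateral eye on Day 1, so L = 0 as planned. The between-eye interval may be adapted, so L = 3 and 6 are also shown as assumptions.

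**Formulas**, treating the treated eye's baseline reading as taken at the dose (for BCVA it may be up to 1 month earlier):

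- non-treated span = D + V
- treated span = V − L
- excess = (D + V) − (V − L) = D + L

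**Results at V = 12 months**

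| D | Non-treated span | Treated span, ratio, excess: L = 0 | L = 3 | L = 6 |
|---|---|---|---|---|
| 6 | 18 | 12, 1.5, 6 | 9, 2.0, 9 | 6, 3.0, 12 |
| 12 | 24 | 12, 2.0, 12 | 9, 2.67, 15 | 6, 4.0, 18 |
| 18 | 30 | 12, 2.5, 18 | 9, 3.33, 21 | 6, 5.0, 24 |
| 24 | 36 | 12, 3.0, 24 | 9, 4.0, 27 | 6, 6.0, 30 |

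**Illustrative size for BCVA.** With an assumed natural decline r, the worsening added to the non-treated row by the parent-study interval alone is r × D / 12. For r = 0.01 to 0.10 logMAR per year, which the documents do not give:

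- D = 6: 0.005 to 0.05 logMAR
- D = 12: 0.01 to 0.10 logMAR
- D = 18: 0.015 to 0.15 logMAR
- D = 24: 0.02 to 0.20 logMAR

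**With Baseline 002 for non-treated eyes**, their span becomes V and the excess becomes V − (V − L) = L: 0, 3 or 6 months for the three values of L. D drops out.

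**Construction also differs.** For mobility course and FST, Baseline 001 is an average, while the treated eye's value is a single latest reading. The mismatch is therefore not purely one of time.

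**The case against.** There is a fair case against reading too much into this.

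- A reader might infer that this is the study's only treated-versus-untreated contrast. It is not. The table in SAP 4.8.1.1 also shows first treated eyes, and these share Baseline 001 with non-treated contralateral eyes. The sentence in 4.2.4 gives that comparison a common starting point, which is a reason to keep it there.
- The SAP does not say that the change tables use the Pre-dose Baseline. Baseline 002 is also defined, and the Efficacy Evaluable Population requires a Baseline 002 BCVA value. A matched change may be intended. This stands, but no text commits to it, and the missing link between tables and baselines needs repair in any case.
- The group FST tables in 4.8.3 are described as mean values, which need no baseline; change appears there in individual-value tables. However, change in FST is a secondary endpoint, and SAP 4.8 promises descriptive statistics for those endpoints. The mobility course section, 4.8.2, is absent from the public text, so its tables cannot be checked.
- No treated-minus-untreated estimate or test is planned, and the BCVA and FST responder analyses of contralateral eyes cover treated eyes only. Setting the drift against the 0.2 or 0.3 logMAR responder cut-offs would therefore suggest a distorted responder rate that the SAP never calculates for non-treated eyes.
- Protocol 10.4 has a looser definition of baseline, allowing data before first dose in either study. The departure is clear against protocol 4.2 and 10.1, less so against 10.4.
- Equal time would not make this a treatment contrast. The decision to treat the contralateral eye is made case by case (protocol 4.2).

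These points limit the reach of the concern. They do not remove the mismatch, which follows from the definitions for any D above zero.

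**Conclusion.** The point holds for BCVA, mobility course and FST wherever the Pre-dose Baseline is used to set treated beside non-treated contralateral eyes. Their changes then differ in elapsed time by D + L, and the D part is avoidable. The month and logMAR figures above are illustrations, since the length of PQ-110-001, any gap before entry and the rate of decline are not in the documents. Direction is also open: progression would favour treated eyes, and practice effects would work against them. It would be wrong to conclude that the plan is biased in favour of treatment by a known amount. This is a correctable flaw in a descriptive display and does not affect the primary safety endpoints.

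**What to change.** In SAP 4.2.4, specify Baseline 002 (Screening/Day 1) for non-treated contralateral eyes in every BCVA, FST and mobility course change table that sets them beside treated contralateral eyes. This agrees with protocol 4.2 and with the SAP's rule for NIRAF, OCI and PLR. Keep Baseline 001 for comparing first treated with non-treated contralateral eyes. State the baseline in the title or footnote of each change table, and show time since baseline where the contralateral eye was dosed later than Day 1. Give the reason for any remaining departure from the protocol in SAP section 5.

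The cost is a sentence or two in the SAP and one more baseline flag in programming; Baseline 002 is already defined, so no new data are needed. The drawbacks are that non-treated eyes appear with two baselines in separate tables, and that a mismatch of L months stays for late-dosed eyes. For mobility course and FST, Baseline 002 may average two readings where the treated eye has one, so a small difference in construction also remains. The comparison stays descriptive and non-randomised.

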### 4.2.1 Study Plan

#### 4.2.1.1 Screening/ Day 1

The Screening/Day 1 visit for this study should be the last visit (EOS visit) of study PQ-110-001, ie, all Screening/Day 1 assessments should take place during the EOS visit of study PQ-110-001. If these visits do not occur at the same time, a separate Screening/Day 1 visit should be

performed as part of PQ-110-002 ([Appendix 1](#)). During the Screening/Day 1 visit, subjects will be assessed according to the eligibility criteria.

Measures of visual function (including BCVA, FST, OCI, and mobility course), and retinal anatomy (OCT) will be assessed a minimum of 1 time prior to the subject receiving study drug. Any pre-dose assessment may be repeated if the results are considered unreliable or of unacceptable quality by the Investigator or if the assessment could not be completed. Additional assessments may be performed at Investigator discretion.

Assessments can be completed over multiple days instead of 1 full day, at the discretion of the Investigator.

The Investigator, in consultation with the Medical Monitor, will decide on subject's enrollment upon assessment of subject's benefit/risk and the subject's meeting of eligibility criteria. Continued subject treatment in this study is desirable, but cannot be guaranteed, since it will depend on the risks and benefit of further treatment on a case-by-case basis, as discussed and agreed upon with the Medical Monitor.

Adverse events considered to be related to the study drug should be taken into account in the benefit/risk assessment.

See [Section 7.0](#) for more details on the screening process.

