#### 4.8.1. BCVA

The BCVA will be assessed using the BVRT and the ETDRS acuity test. The best BCVA reading (ie, smallest numerical value in logMAR) for the first treated eye (based on ETDRS/BVRT) at Screening is considered the baseline BCVA (see also Section 4.2.4).

BCVA is assessed using an ETDRS chart, or the BVRT (Bailey et al, 2012). ETDRS provides logMAR values using on-chart assessments (i.e., logMAR values  $< +1.7$ ). BVRT provides logMAR values based on off-chart assessments (i.e., logMAR values  $\geq +1.7$ ), which is meant for subjects who cannot read letters.

For subjects whose vision cannot be assessed with BVRT Single Tumbling E or Grating Acuity charts yielding logMAR values, the following BCVA measures can be provided based on BVRT: white field projection (WFP) and black and white discrimination (BWD). The measures of WFP and BWD represent more qualitative levels of vision as described by Bailey et al. 2012. For this study, imputed logMAR values will be used for WFP and BWD, as outlined in Table 2. For subjects with vision equal or worse than light perception (LP) data can be collected through the clinical practice assessment

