### 4.8.1.2. Responder Analysis for Treated Contralateral Eye

A responder analysis will be summarized on overall group and performed on all contralateral eyes treated in PQ-110-002 with the following definitions of responders:

- BCVA change from baseline for on-chart subjects (ie, BCVA < 1.7 logMAR based on ETDRS):
  - Equal or better than -0.2 logMAR, smaller values are better
  - Equal or better than -0.3 logMAR, smaller values are better
- BCVA change from baseline for off-chart subjects (ie, BCVA  $\geq$  1.7 logMAR based on BRVT/clinical practice assessment):
  - leading to a categorical change in VA category according to Holladay VA reference scale (Section 8):
    - From LP to HM or better, ie,
      - from logMAR 4 (clinical assessment) or logMAR 3.5 (BWD result from BRVT) to logMAR 3 (clinical assessment) or better (BRVT)
      - from logMAR 3.2 (WFP result from BRVT) to logMAR 2.9 or better (BRVT)
    - From HM to CF or better, ie,:
      - from logMAR 3 (if only clinical assessment result available) to logMAR 2 (if only clinical assessment result is available) or better (BRVT), OR:

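### The BCVA baseline for treated contralateral eyes is the better of two readings when two exist, with no visible matching rule at follow-up, so change may be shifted towards worsening

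*SAP*

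**What the plan says.** SAP 4.2.4 defines the pre-dose BCVA baseline of a treated contralateral eye as "the best of the two most recent BCVA values available before the first dose of treatment with sepofarsen in that respective eye", limited to readings "in a maximum time-window of 1 month before dosing". It adds: "If only one observation is available on or prior to the subject's first dose, that observation will be used as the pre-dose baseline value". SAP 4.8.1, writing about the first treated eye, explains what best means: "The best BCVA reading (ie, smallest numerical value in logMAR".

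Two pre-dose readings are not required. Protocol 4.2.1.1 says that visual function, including BCVA, "will be assessed a minimum of 1 time prior to the subject receiving study drug".

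After baseline, SAP 4.2.10 considers scheduled and unscheduled data in a window of plus or minus 30 days, but gives no visible rule for choosing among several readings. SAP 4.2.9.2 takes the single closest value when the window is empty. SAP 4.8.1.1 then summarises change by eye and visit. SAP 4.8.1.2 counts on-chart responders among treated contralateral eyes at -0.2 and -0.3 logMAR, the stricter criterion being "Equal or better than -0.3 logMAR, smaller values are better".

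Protocol 10.4 allows baseline to be the most recent measurement and/or the one showing the highest visual function. The BCVA definitions of Baseline 001 and Baseline 002 are not visible in the public text.

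**The concern.** The smaller of two noisy logMAR readings lies, on average, below the eye's true level. If the follow-up value is not selected in the same way, the whole of that gap enters the change score as apparent worsening. Eyes with only one baseline reading carry no such shift, so shifted and unshifted eyes can sit in the same mean and the same responder rate. At stake are the mean BCVA change and the -0.2 and -0.3 responder rates in the eyes first treated in this study, of which there are at most 11.

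**Working it through.** The plan states no SD, test-retest figure or power for BCVA, so there is no figure of its own to reproduce.

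**Inputs.** From the documents: the best-of-two rule with its one-reading fallback (SAP 4.2.4), the on-chart threshold of -0.3 (SAP 4.8.1.2), and a maximum of 11 subjects (Protocol 5.1). Assumed: normal, independent reading errors with SD s, ranged from 0.05 to 0.20 logMAR, and one unselected reading per follow-up visit.

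**Shift.** For two independent normal errors, E[min] = -s/√π = -0.564s. The shift in change (follow-up minus baseline) is therefore +0.564s, towards worsening. If the two baseline errors correlate at ρ, it is s√((1-ρ)/π), which is 0.399s at ρ = 0.5. If half the eyes have two readings, the average shift over all eyes halves.

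| s (logMAR) | Two readings, independent | Two readings, ρ = 0.5 | Half the eyes with two readings, independent |
|---|---|---|---|
| 0.05 | 0.028 | 0.020 | 0.014 |
| 0.10 | 0.056 | 0.040 | 0.028 |
| 0.15 | 0.085 | 0.060 | 0.042 |
| 0.20 | 0.113 | 0.080 | 0.056 |

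**Precision.** Var[min] = s²(1 - 1/π) = 0.682s², against 1.000s² for one reading and 0.500s² for the mean of two. Best-of-two thus achieves (1 - 0.682)/(1 - 0.500) = 64% of the variance reduction that averaging gives. Its mean squared error about the true acuity is 0.318s² + 0.682s² = 1.000s², the same as one reading. With one follow-up reading added, the root mean squared error of change is √2.000 s = 1.41s for best-of-two and √1.500 s = 1.22s for the mean. A simulation of 2,000,000 draws gave -0.563 for the mean of the minimum and 0.683 for its variance, in units of s and s².

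**Responders, on-chart eyes.** With a true change of exactly -0.3, the eye meets the criterion only if the follow-up error is the smallest of three exchangeable errors. That probability is 1/3, or 33%, for any s, against 50% with the mean. The other rates come from the simulation:

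| True change | s | Best of two | Mean of two |
|---|---|---|---|
| -0.4 | 0.05 | 87% | 95% |
| -0.4 | 0.10 | 63% | 79% |
| -0.4 | 0.15 | 53% | 71% |
| -0.4 | 0.20 | 48% | 66% |
| 0 (false responder) | 0.15 | 2.3% | 5.1% |

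A single-reading baseline gives 7.9% false responders in the last case.

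**Against sampling error.** With 11 eyes, all with two readings, the ratio of shift to the measurement-error SE of mean change is 0.564/√(1.682/11) = 0.564/0.391 = 1.44. True differences between eyes in their change would enlarge the SE and lower this ratio.

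**The case against.** The strongest defence is that the rule is permitted and errs in the safe direction. Protocol 10.4 allows the highest-function measure, and SAP 4.8.1 uses the best reading for first treated eyes. In an open-label study without a concurrent control group, a baseline that makes improvement harder to show and cuts false responders is a defensible choice. The study is small and descriptive, and SAP 4.8.1.1 provides individual values and a full BCVA listing, so a reader can inspect the data. All of this stands, and it limits the consequences. It does not remove the point: a descriptive estimate should not carry an avoidable shift, and the shift may differ between eyes in the same table.

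The premise can also be challenged. One unselected reading per follow-up visit is an inference, since the schedule of events is not visible. If follow-up were also best-of-two with the same error structure, the shift would cancel. That stands too, and is why the conclusion is conditional. The normal model also fits off-chart eyes poorly, because their responder rules rest on category changes and partly on assigned values, so the responder rates above apply to on-chart eyes only.

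A reader might infer that the SAP already averages repeat mobility and FST readings for this eye, so that BCVA is the odd one out. It does not. For those two measures "the average of measurements at pre-dose in study PQ-110-001 is considered as baseline 001", and Baseline 002 averages the last two readings when they are close enough in time. For the treated contralateral eye's pre-dose baseline, however, SAP 4.2.4 takes the most recent mobility and FST values.

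**Conclusion.** The point holds in conditional form. As written, the rule selects the better of two readings at baseline, does so only in eyes that have two, and has no visible counterpart after baseline. If follow-up values are single and unselected, change is shifted towards worsening by 0.564s in eyes with two readings and by 0 in the others. That is about 0.03 to 0.11 logMAR for assumed s of 0.05 to 0.20, and about 0.02 to 0.08 if the baseline errors correlate at 0.5. For an on-chart eye with a true change of -0.3, the chance of counting as a responder is 33% instead of 50%. The second reading does reduce variance, but best-of-two gains nothing over one reading in mean squared error.

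Two stronger conclusions are tempting and unsupported. One is that the error has a known size: the documents give neither s nor the number of eyes with two readings, and the protocol's minimum of one pre-dose assessment means that some or all eyes may have no shift. The other is that a planned safety analysis of BCVA loss in these eyes is inflated: BCVA is a secondary efficacy endpoint, and the visible worsening thresholds in SAP 4.8.1.3 apply only to first treated eyes.

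**What to change.** In SAP 4.2.4, use the mean of the two readings within the 1-month window as the BCVA baseline for treated contralateral eyes, or apply the same selection at baseline and at every later visit. State how many BCVA readings are taken at each follow-up visit and which one is analysed. Report how many treated contralateral eyes had one and how many had two baseline readings. Show mean BCVA change and the -0.2 and -0.3 responder rates side by side under the mean and the best-of-two baseline.

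The cost is SAP wording and one extra table, with no new data. The downside of the mean is that the rule may then differ from the best-reading rule for first treated eyes in SAP 4.8.1 and from the baseline definition in Protocol 10.4. The side-by-side table covers that, and SAP Section 5 should record the departure from the protocol.
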